22.9 Appendix 9 – POSAS Observer Scale

POSAS Observer scale

[figure not shown]
[figure not shown]
The Patient and Observer Scar Assessment Scale v2.0 / EN

Date of examination:

Observer

Research / study:

Identification number

Explanation

The observer scale of the POSAS consists of six items (vascularity, pigmentation, thickness, relief, pliability and surface area). All items are scored on a scale ranging from 1 ('like normal skin') to 10 ('worst scar imaginable'). The sum of the six items results in a total score of the POSAS observer scale. Categories boxes are added for each item. Furthermore, an overall opinion is scored on a scale ranging from 1 to 10. All parameters should preferably be compared to normal skin on a comparable anatomic location.

Explanatory notes on the items

- **VASCULARITY** Presence of vessels in scar tissue assessed by the amount of redness, tested by the amount of blood return after blanching with a piece of Plexiglas
- **PIGMENTATION** Brownish coloration of the scar by pigment (melanin); apply Plexiglas to the skin with moderate pressure to eliminate the effect of vascularity
- **THICKNESS** Average distance between the subcutical-dermal border and the epidermal surface of the scar
- **RELIEF** The extent to which surface irregularities are present (preferably compared with adjacent normal skin)
- **PLIABILITY** Suppleness of the scar tested by wrinkling the scar between the thumb and index finger
- **SURFACE AREA** Surface area of the scar in relation to the original wound area

Timing of Suture Removal to Reduce Scarring in Skin Surgery

22.10 Appendix 10 – POSAS Patient Scale

POSAS Patient scale

[figure not shown]
[figure not shown]
The Patient and Observer Scar Assessment Scale v2.0 / EN

Date of examination:

Observer:

Location:

Identification number

1 = no, not at all

yes, very much = 10

1 2 3 4 5 6 7 8 9 10

HAS THE SCAR BEEN PAINFUL THE PAST FEW WEEKS?

HAS THE SCAR BEEN ITCHING THE PAST FEW WEEKS?

ANSWER

11. *What is the primary purpose of the following statement?*

Digitized by the Internet Archive in cooperation with the Internet Archive BookBot Project

IS THE THICKNESS OF THE SCAR DIFFERENT FROM YOUR NORMAL SKIN?

10 of 10

© 2013 Pearson Education, Inc. All Rights Reserved. May not be copied, scanned, or duplicated, in whole or in part. Due to electronic rights, some third party content may be suppressed from the eBook and/or eChapter(s). Editorial review has determined that any suppressed content does not materially affect the overall learning experience. Pearson Education, Inc. reserves the right to remove additional content at any time if subsequent rights restrictions require it.

[figure not shown]
Timing of Suture Removal to Reduce Scarring in Skin Surgery

22.11 Appendix 11 – Numerical Visual Analogue Scale (VAS)

Numerical Visual Analogue Scale (VAS)

Participant Number:

Please make a mark on the line below where you feel the appearance of your scar lies, **with regards to suture marks.**

Timing of Suture Removal to Reduce Scarring in Skin Surgery

22.12 Appendix 12 – GP letter

Dermatology Department
Heavitree Hospital
[name]
Exeter
[name]
[contact]

INSERT DATE

Dear INSERT NAME OF GP

TIMING OF SUTURE REMOVAL TO REDUCE SCARRING IN SKIN SURGERY

Re: PARTICIPANT DETAILS

The above named person has kindly agreed to take part in this research study. The objective of the study is to determine whether suture removal at day 7 or day 10 post skin surgery will affect suture marks and overall cosmesis of scars.

Your patient has been chosen to take part because they have been booked for a wide local excision for their skin cancer surgery.

Should you have any queries about this, please do not hesitate to contact me on the details above.

Yours Sincerely,

[name]
Academic Foundation Doctor
Royal Devon and Exeter Hospital NHS Trust

Timing of Suture Removal to Reduce Scarring in Skin Surgery

22.13 Appendix 13 – Standard Operating Procedure (SOP) for Suture Removal

Standard Operating Procedure (SOP) for Suture Removal

Aim:

The nurse or healthcare assistant is able to assess the wound post operatively, remove the superficial sutures appropriately and recommend simple post-operative wound care

[figure not shown]
Procedure:

1. Confirm the patients identity and gain consent for removal of sutures
2. Wash hands and prepare procedure trolley surface aseptically with correct equipment:
 - a. Disposable Fine tipped non toothed forceps
 - b. Dressing pack – containing sterile gloves and gauze
 - c. Disposable sharp surgical scissors
 - d. Sterile normal saline if required
3. Wash hands and use non-sterile gloves to remove current dressing (if any)
4. The wound should specifically be checked for signs of dehiscence, infection or poor wound healing. If this is the case, medical advice should be sought
5. If the wound shows signs that it may dehisce if sutures are removed at the time, then consider keeping sutures in for removal at a later date at the discretion of the healthcare professional. These patients will be excluded from the study. If this is the case, it is important that you let the study team know by contacting us on the below details.
6. Removal of simple percutaneous interrupted sutures:
 - a. Wash hands and don sterile gloves
 - b. Gently grasp the knot of a suture with forceps and raise it slightly
 - c. Place the tip of the suture scissors directly under the knot or on the side close to the skin
 - d. Gently cut the suture and pull it out gently across the wound with the forceps
 - i. Remove the suture across the wound to minimise any exposed suture passing through the skin and wound during the removal, this can lead to infection. Cutting the correct part of the suture (part directly under the knot on the side closest to the skin), will bypass this from happening
 - e. Place steri-strips on the sites that sutures have been removed. These are applied in opposite directions with a small amount of tension to take tension away from the wound. Educate patient to let the steri-strips fall off naturally (usually 1-2 days). No further treatment to the wound should be required.

Timing of Suture Removal to Reduce Scarring in Skin Surgery

- f. Continue to remove sutures until all sutures have been removed
- g. The application of a suitable wound dressing can be applied at the healthcare professionals discretion
- h. Discard sutures as per local policy and record the intervention in the medical notes
- i. Dispose any sharps and used instruments safely according to trust policy

If there have been any early post-operative complications, such as dehiscence, infection or poor wound healing, please could you contact the study organisers on the details below.

[name] (CI), [name] (PI), [name] (PI)
Dermatology Department
Heavitree Hospital
Royal Devon and Exeter NHS Foundation Trust
[name]
[name]
[contact]

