16.4 Randomization and Blinding

Timing of Suture Removal to Reduce Scarring in Skin Surgery

Patients will be randomized into two groups following acceptance into the trial. A dermatology nurse, independent to the research trial and not involved in data collection or analysis, will use a random number generator to prepare 60 sealed envelopes, labelled 'participant 1' to 'participant 60'. These sealed envelopes will contain a slip of paper that either says 'suture removal at 7 days group' or 'suture removal at 10 days group'. During preparation of these envelopes using the random number generator, an odd number produced will be 'suture removal at 7 days group' and an even number will be 'suture removal at 10 days group'. The nurse who prepares these envelopes will be independent of the research trial to avoid any selection bias and maintain concealment. They will also have completed a 'Good Clinical Practice' (GCP) certificate. The surgeon and members of the research team involved in data gathering and analysis will be blinded to allocation.

After written consent to the trial has been gained, and excision of the lesion performed, the patient will leave the theatre room alongside one of our dermatology nurses/HCAs who is independent of the research team in order to maintain concealment and prevent selection bias. The patient and nurse/HCA will open one of the sealed envelopes, in numbered order, to reveal which arm of the trial they have been allocated to. The patient will be requested not to disclose which arm of the trial they were in. The theatre nurse or healthcare assistant will then discuss the post-operative wound care and timing of suture removal with the patient.

Patient blinding is not feasible as patients need to know which day to have their sutures removed post-surgery.

Before the patient leaves the department, an appointment will be booked with their GP for suture removal at either 7 or 10 days. If their GP does not have the capacity to remove the sutures on the given day, an appointment will be booked within the dermatology department on the given day for suture removal.

If the patient cannot attend the appointment for suture removal specifically on day 7 or 10, they will be removed from the study.

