16.6 Data Collection at 3 Month Follow Up

Patients will be booked in for a 3 month follow-up appointment, as per their standard care pathway. Data collection at 3 month follow up will include completing a patient and observer scar assessment scale (POSAS) with regards to overall scar cosmesis, and also a visual analogue scale (VAS) in relation to suture marks specifically. We have chosen these tools as they are validated, well known scales to characterise scars subjectively and objectively [10].

The patient will be asked about any post-operative complications that were not detected at suture removal including wound infection, dehiscence, and significant post-operative bleeding (defined as bleeding requiring assessment by a healthcare professional). Assessment will be carried out by a member of the research team who will be blinded to trial allocation.

Photographs of the scar will be taken at the follow-up visit using the departmental camera to allow review of scar assessment at a later date if required. This will be directly uploaded onto their electronic patient record in line with Trust policy. Patients will be verbally consented for this at time of follow up, as per usual practice.

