22.8 Appendix 8 – Data Collection Form

Data Collection Form	
Participant Number:	
Data Collection at Time of Surgery	
Age:	
Ethnicity:	
Clinical diagnosis (pre-op):	
Site:	
Length of wound (mm):	
Width of wound (mm):	
Number and type of interrupted subcuticular sutures:	
Number and type of interrupted percutaneous sutures:	
Drug history (immunosuppressants or anticoagulants):	
Diabetic diagnosis:	
Smoking history:	
History of keloid scar or hypertrophic scarring:	
Normal length of time recommended for suture removal in this case:	

Timing of Suture Removal to Reduce Scarring in Skin Surgery

Data Collection at 3 Month Follow-up			
Stitch marks visible (yes/no):			
POSAS:	Patient scale	Pain:	
		Itch:	
		Colour:	
		Stiffness:	
		Thickness:	
		Irregular:	
		Overall Opinion (not part of total score):	
	Total:		
	Observer Scale	Vascularity (pale; pink; red; purple; mix):	
		Pigmentation (hypo; hyper; mix):	
Thickness (thicker; thinner):			
Relief (more; less; mix):			
Pliability (Supple; stiff; mix):			
Surface area (expansion; contraction; mix):			
Overall Opinion (not part of total score):			
Total:			
VAS:			
Wound infection (defined using CDC criteria for surgical site infection)*:			
Wound dehiscence:			
Significant post-operative bleeding:			
Any other comments:			
* Infection occurs within 30 days after the operation and infection involves only skin and subcutaneous tissue of the incision and at least one of the following: 1.Purulent drainage with or without laboratory confirmation, from the superficial incision 2.Organisms isolated from an aseptically obtained culture of fluid or tissue from the superficial incision			

Timing of Suture Removal to Reduce Scarring in Skin Surgery

- 3. At least one of the following signs or symptoms of infection: pain or tenderness, localized swelling, redness, or heat and superficial incision is deliberately opened by surgeon, unless incision is culture-negative
- 4. Diagnosis of superficial incisional SSI made by a surgeon or attending physician

Timing of Suture Removal to Reduce Scarring in Skin Surgery

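### The only graded suture-mark measure is marked by patients who know their arm; a VAS marked by the blinded assessor at the same visit would be a cheap addition, with one minor safeguard for that assessor's blinding.

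*Combined protocol and SAP*

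**What the plan says.** Section 16.6 plans the POSAS for overall cosmesis and a VAS for suture marks at 3 months. On the rater it says: "Assessment will be carried out by a member of the research team who will be blinded to trial allocation". Section 16.4 sets the wider rule: "The surgeon and members of the research team involved in data gathering and analysis will be blinded to allocation". On patients, the same section says: "Patient blinding is not feasible as patients need to know which day to have their sutures removed post-surgery".

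The instruments are in the appendices:

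- Appendix 11 addresses the VAS to the patient and ties it to suture marks: "Please make a mark on the line below where you feel the appearance of your scar lies".
- Appendix 9 lists the blinded rater's graded items: "The observer scale of the POSAS consists of six items (vascularity, pigmentation, thickness, relief, pliability and surface area".
- Appendix 8 carries an item that begins "Stitch marks visible (yes/no", with no rater named, and a single line for the VAS.

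Objective 1 takes the presence or absence of suture marks as the outcome for sizing the definitive trial. Section 17 adds that mean or median differences and SDs from continuous data will also inform that sizing. Section 16.6 provides for photographs at follow-up, with later review optional.

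The suture-removal SOP (Appendix 13) asks the person removing the sutures: "If there have been any early post-operative complications, such as dehiscence, infection or poor wound healing, please could you contact the study organisers". The contacts it lists are the chief investigator and two principal investigators. Section 16.4 fixes the removal day: "If the patient cannot attend the appointment for suture removal specifically on day 7 or 10, they will be removed from the study".

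**The concern.** Whether a faint suture mark counts, and how bad it looks, is a matter of judgement, and the stated hypothesis favours removal at 7 days. A patient who knows the removal day may score accordingly. If a graded suture-mark scale is later considered for the definitive trial, this study would supply an SD and a between-arm difference from unblinded raters only, with nothing blinded to set beside them. Objective 6 is to learn the characteristics of the proposed measures. How far patient and blinded scores agree is a natural part of that, and the plan as written cannot show it.

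The second matter is smaller. The SOP sends complication reports from the removal visit to three senior team members. The day of such a visit is tied to the arm, and the sections available for review do not say whether a recipient may later rate that patient's scar.

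**Working it through.** **The plan's own figure.** Section 18.4 gives 59 participants to see a problem of probability 0.05 at least once with about 95% certainty. ln(1 − 0.95) / ln(1 − 0.05) = 58.40, which rounds up to 59; the approximation 3/p gives 3/0.05 = 60. The figure reproduces, and nothing below changes it.

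**Who rates suture marks, and blinded or not.**

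| Measure | Rater | Blinded? | Graded? | Specific to suture marks? |
|---|---|---|---|---|
| VAS (Appendix 11) | Patient, from its wording | No (16.4) | Yes | Yes |
| Yes/no item (Appendix 8) | Not named; 16.6 implies the assessor | Yes, by implication | No | Yes |
| POSAS observer items (Appendix 9) | Assessor | Yes (16.6) | Yes | No, 0 of 6 |
| Photographs (16.6) | None planned | – | None planned | – |

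The POSAS relief item could partly reflect suture marks but is not specific to them. No planned measure is at once blinded, graded and specific to suture marks.

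**What a blinded VAS would yield.** Inputs: 30 analysable patients per arm (Section 18.4), no losses and normal data (both assumed). The pooled SD has 30 + 30 − 2 = 58 degrees of freedom.

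- 95% limits as multiples of the estimate: √(58/χ²₀.₉₇₅) = 0.847 and √(58/χ²₀.₀₂₅) = 1.222.
- A sample size for a mean difference is proportional to SD², so the limits for the size are 0.847² = 0.717 and 1.222² = 1.493 times the estimate.

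The patient VAS has the same relative precision under these assumptions. The gain is an SD and a difference from blinded raters, not a tighter interval.

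**The SOP route.** A patient stays in only if sutures come out on day 7 or day 10, and 10 − 7 = 3 days. Given the surgery date, a removal-visit report received before day 10 can come only from the 7-day arm. A later report is ambiguous unless it states the visit day. The SOP asks for neither a date nor same-day contact. Patients whose sutures are kept in are excluded (SOP step 5), so only those with a complication who remain in the study matter.

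The documents give no complication rate. Assume 2% to 15%, with 50% to 100% of those patients staying in:

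- Lowest: 60 × 0.02 × 0.50 = 0.6 patients. Highest: 60 × 0.15 × 1.00 = 9 patients.
- Per arm of 30: 0.3 to 4.5 patients. The largest possible shift in an arm's yes/no proportion is 0.3/30 to 4.5/30, or 1 to 15 percentage points.
- For comparison, the 95% half-width at 50% with n = 30 is 1.96 × √(0.25/30) = 17.9 points.

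The range is a ceiling. It takes every report as revealing the arm and its recipient as the assessor, and its upper shift needs every affected rating to change in the same direction.

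**The case against.** The best defence is that the plan already blinds what it says it will size on. The research question is incidence, Objective 1 names the yes/no outcome, and Section 16.6 implies that the blinded assessor records it. Section 17's sentence on differences and SDs is general to continuous data and does not name the VAS as a future endpoint. Objective 6 covers the proposed measures and does not call for another. The patient VAS is a legitimate patient-reported outcome in a study that says the impact on patients is unknown. The photographs could support a blinded graded rating later.

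All of that stands. It makes the assessor VAS an improvement and not the repair of an error. It does not remove the gap: no blinded graded rating is planned, and the photographs have neither a rater nor a scale assigned.

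A reader might also infer from the SOP that the 3-month assessors will be unblinded. The documents do not support that. Sections 16.4 and 16.6 require blinding, and nothing shown says that the chief investigator or a principal investigator will assess. Section 7 (Project Management) and the flow chart were not available for review and may already separate the roles. The timing clue also requires prompt receipt, knowledge of the surgery date, and recall about three months later.

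**Conclusion.** The point holds as a cheap improvement. As planned, there are 0 blinded graded ratings of suture marks; the change gives up to 60, from visits already scheduled. The SD and sizing multiples above assume 30 per arm, normal data and no losses, and matter only if the definitive trial considers a graded endpoint.

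It would be wrong to conclude that the sizing basis in Objective 1 is unblinded, or that the patient VAS is invalid. The first is blinded by implication and needs only a rater label; the second should stay.

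The SOP matter is a minor safeguard. The count of 0.6 to 9 patients rests entirely on assumed rates and is an upper limit on ratings affected under those rates. If Section 7 or the flow chart already keeps report recipients from assessing, this part falls away; the part on the VAS does not.

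**What to change.** In Section 16.6 and Appendix 8:

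1. Have the blinded assessor already at the 3-month visit also mark a suture-mark VAS, before asking about complications.
2. Label the yes/no item as completed by that assessor.
3. Report the patient VAS as an unblinded patient-reported outcome beside the blinded ratings, and leave the choice of endpoint to the definitive trial.

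As the safeguard, leave the SOP reporting route unchanged. State in Section 16.6 that a team member who received a removal-visit complication report for a patient does not rate that patient where another blinded member is available; otherwise, the assessor's knowledge of the arm is recorded.

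The cost is one extra form line, a rater label, short additions to Section 16.6, and about one minute per visit (assumed), or 60 × 1 = 60 minutes in all. The safeguard puts a small constraint on who rates a few patients. The sample size does not change.
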